8.1 Data Collection

- REDCap electronic data capture
- Standardized photography with measurement software
- Secure storage of identifiable information

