2.1 Primary Objective

To assess the efficacy of intralesional Gardasil 9 in treating genital condylomata through:

- Reduction in wart number
- Reduction in mean wart size
- Reduction in total skin area covered by warts

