2.2 Secondary Objectives

- Evaluate patient-centered outcomes using:
 - CECA (Specific Questionnaire for Condylomata Acuminata)
 - Dermatology Quality of Life Index (DLQI)
 - Global patient satisfaction (1-5 scale)
- Assess tolerability of intralesional Gardasil 9

3. Study Design

- Prospective, open-label, single-arm proof-of-concept study
- Duration: 12 weeks per participant
- Sample size: 10 participants
- Two treatment visits (Week 0 and Week 4)

4. Study Population

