5.1 Visit Schedule

Visit 1 (Week 0)

1. Informed consent
2. Baseline data collection:
 - Demographics
 - Medical history
 - Medication review
 - Condylomata history
3. Pregnancy test if applicable
4. Photography and measurements
5. Questionnaires (CECA, DLQI)
6. Shave biopsy ($\leq 5 \times 5 \text{ mm}$) for histologic confirmation
7. First Gardasil 9 injection
8. 15-minute observation period

Phone Follow-up 1 (Week 1)

- Assess adverse effects
- Arrange follow-up if needed

Visit 2 (Week 4)

1. Assessment of treatment response
2. Photography and measurements
3. Questionnaires (CECA, DLQI)
4. Second Gardasil 9 injection if indicated

5. 15-minute observation period

Phone Follow-up 2 (Week 5)

- Assess adverse effects
- Arrange follow-up if needed

Visit 3 (Week 12)

1. Final assessment
2. Photography and measurements
3. Questionnaires (CECA, DLQI, satisfaction)

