7.1 Sample Size

Pilot study of 10 participants; no formal sample size calculation as effect size is unknown.

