7.3 Primary Endpoint Analysis

Paired t-tests comparing baseline to week 12:

- Wart number
- Mean wart size
- Total skin area covered by warts

Significance level: $\alpha = 0.05$

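### The plan does not say who measures the warts, from what source, or whether images are read without knowledge of visit, so assessor expectation could contribute to all three primary reductions

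*Combined protocol and SAP*

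**What the plan says.** Section 3 of the combined protocol and SAP describes a "Prospective, open-label, single-arm proof-of-concept study". The primary outcomes (sections 2.1 and 7.3) are wart number, mean wart size and total wart area. Section 7.3 analyses each by "Paired t-tests comparing baseline to week 12", so the null hypothesis is zero mean change.

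On measurement the plan is brief. Section 5.1 lists "Photography and measurements" at Weeks 0, 4 and 12. Section 8.1 adds "Standardized photography with measurement software". Nothing names the assessor, assigns each outcome to examination or image, or states what the assessor knows about the visit. Section 9.2 mentions coding for specimens but not for images. Quality control in section 8.2 consists of data review by the PI, range and validation checks, and backup. It includes no check of agreement between or within assessors.

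**The concern.** Measurement software can compute an area once a border is drawn, but the plan does not say that finding or outlining the warts is automated. Deciding whether a flat or resolving lesion still counts, or where its edge lies near injected or biopsied skin, plausibly needs judgement. In an open-label study the person judging may expect improvement.

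A concurrent control read the same way would absorb part of such a tendency. Here there is none, so a systematic difference between how baseline and Week 12 are read cannot be told apart from treatment effect. Total area depends on number and size, so the three outcomes would tend to share the error, and agreement among them would be weak corroboration. None of the checks in section 8.2 would detect a consistent shift that stays within plausible ranges.

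**Working it through.** **Setting the sections side by side.** Section 5.1 makes measurement a step of each visit. If it is done on the patient, the assessor necessarily knows the visit. If it is done from images, section 8.1 contains nothing that hides the visit. Either route leaves room for expectation, but the plan does not say which route applies to which outcome.

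**Size of the consequence.** The plan has no figure to reproduce: section 7.1 says "Pilot study of 10 participants; no formal sample size calculation as effect size is unknown", and no SD, effect size or power is given. The calculation below is therefore illustrative.

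Inputs from the plan:
- n = 10 (sections 3 and 7.1), so df = 9.
- Paired t-test against zero change, significance level 0.05 (section 7.3). Sidedness is not stated; two-sided is assumed.

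Assumptions, not in the plan:
- True mean change is zero, differences are normal, and all 10 participants have Week 12 values.
- The reading shift is d = (mean shift between baseline and Week 12 readings) / (SD of paired differences), over a range of values.

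Step 1. The critical value is t(0.975, 9) = 2.262. A result is significant when the observed mean change exceeds 2.262/√10 = 0.715 SD.

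Step 2. The expected observed change is the true change plus the shift, here 0 + d. The test statistic is noncentral t with 9 df and noncentrality λ = d√10. The chance of a falsely significant reduction is P(T > 2.262).

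Step 3. For at least one of three outcomes with the same d on each, independence gives 1 − (1 − p)³. For correlation 0.8 the figure comes from a simulation of 100,000 trials.

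| d (assumed) | λ = d√10 | p, one outcome | at least one of three, independent | at least one of three, correlation 0.8 |
|---|---|---|---|---|
| 0 | 0 | 2.5% | 7.3% | 5.3% |
| 0.1 | 0.316 | 4.7% | 13.4% | not simulated |
| 0.2 | 0.632 | 8.2% | 22.6% | 15.0% |
| 0.3 | 0.949 | 13.4% | 35.0% | 23.0% |
| 0.5 | 1.581 | 29.3% | 64.6% | 44.5% |

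For example, at d = 0.3 under independence: 1 − (1 − 0.1337)³ = 0.350.

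These are rates for significant reductions only, which is the error at issue. Counting significance in either direction, the per-outcome rate goes from 5% at d = 0 to 13.6% at d = 0.3 and 29.3% at d = 0.5.

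Step 4. If masked reading removes the differential shift, d = 0 and the per-outcome rate returns to 2.5% under the same null.

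**The case against.** Someone reading the plan might infer that the assessor is unmasked and knows each image's visit, and that all three outcomes are measured from photographs. The documents support neither statement. They are silent on who measures, when, and with what knowledge. Section 5.1 names photography and measurement together without tying one to the other, so counts or sizes may be taken on the patient. The defect is an unspecified procedure, not a documented unmasked reading. This stands, and it limits how the point can be put.

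The magnitudes can also be challenged. Nothing in the documents supports a shift of 0.3 or 0.5 SD. The SD of paired differences includes variation in response between participants, so 0.3 SD need not be a small tracing error. At 0.1 SD the rate rises only from 2.5% to 4.7%. This stands too: the table shows sensitivity to bias, not its likely size.

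The zero-change scenario is narrow. Section 1.2 cites clearance of 81% and 63% with a bivalent vaccine, and section 4.1 requires lesions larger than 3 mm. Complete disappearance of such a lesion leaves less room for judgement than partial shrinkage, and number may be less exposed than size or area. That is fair. However, where there is a true response, a shift still adds to its estimated size.

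Finally, this is a declared pilot of 10 participants, and masking leaves its main limitation in place. Spontaneous regression, regression to the mean and the baseline shave biopsy would still be mixed with treatment effect. That is correct, but differential reading is one bias that can be reduced without adding an arm, and section 7.3 does run tests at 0.05.

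**Conclusion.** The concern holds as a gap in specification. For its three primary outcomes the plan leaves open the assessor, the source of measurement and the assessor's knowledge of the visit. In a single-arm, open-label study tested against zero, assessor expectation could therefore contribute to an apparent reduction in all three. With n = 10, a two-sided 0.05 test and no true change, assumed shifts of 0.1, 0.3 and 0.5 SD raise the per-outcome chance of a falsely significant reduction from 2.5% to about 4.7%, 13.4% and 29.3%. Those shifts are assumptions, and the documents do not establish that any bias occurs. The gap should be closed because closing it is cheap and it touches every primary outcome. It does not invalidate the study.

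**What to change.** In sections 8.1 and 7.3, state that the primary-analysis values of wart number, mean size and total area come from the standardized photographs, read in one batch after the last Week 12 visit. Remove date and visit labels, assign random codes and shuffle the order. Existing study staff can do the reading, preferably someone who did not take that participant's visit-day measurements, since remembered values or a recognised participant could defeat the masking. Keep visit-day measurements for clinical use and as a sensitivity analysis.

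The cost is one re-measurement of about 30 image sets (10 participants × 3 visits), a few hours of staff time, with no added visit or reader. There are two further downsides. Masking will be incomplete where a biopsy scar, healing or a recognisable participant reveals the visit. If any outcome was to be counted on the patient, its source changes, and the plan should say so.

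The text should also acknowledge that masking does not address spontaneous regression, regression to the mean or the effect of the shave biopsy, which remain limits of the single-arm design.

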8.2 Quality Control

- Monthly data review by PI
- Range checks and validation rules in REDCap
- Regular backup of study data

9. Ethical Considerations

9.1 Risk Mitigation

- Pre-treatment with topical anesthetic
- Close monitoring post-injection
- Direct access to study team
- Emergency equipment available
- ACLS-certified physicians present

9.2 Confidentiality

- Coded study numbers for specimens

- Secure data storage
- Limited access to identifiable information

10. Timeline

- Study Duration: Approximately 6-12 months
- Individual Participation: 12 weeks
- Data Analysis: 3 months post-completion
- Manuscript Preparation: 6 months post-analysis
